10.3.1 Definition of AE

AE Definition

An AE is any untoward medical occurrence in a patient or clinical study participant, temporally associated with the use of study treatment, whether or not considered related to the study treatment.

NOTE: An AE can therefore be any unfavorable and unintended sign (including an abnormal laboratory finding), symptom, or disease (new or exacerbated) temporally associated with the use of study treatment.

Events Meeting the AE Definition

- 1. Any abnormal laboratory test results or other safety assessments (e.g., ECG, radiological scans, vital signs measurements), including those that worsen from baseline, considered clinically relevant in the medical and scientific judgment of the investigator.
- 2. Exacerbation of a chronic or intermittent pre-existing condition including either an increase in frequency and/or intensity of the condition.
- 3. New conditions detected or diagnosed after signature of the ICF even though it may have been present before the start of the study.
- 4. Signs, symptoms, or the clinical sequelae of a suspected drug-drug interaction.
- 5. Signs, symptoms, or the clinical sequelae of a suspected overdose of either study treatment or a concomitant medication. Overdose per se will not be reported as an AE/SAE unless it is an intentional overdose taken with possible suicidal/self-harming intent. Such overdoses should be reported regardless of sequelae.
- 6. For efficacy studies, include:
- 7. "Lack of efficacy" or "failure of expected pharmacological action" per se will not be reported as an AE or SAE. Such instances will be captured in the efficacy assessments. However, the signs, symptoms, and/or clinical sequelae resulting from lack of efficacy will be reported as AE or SAE if they fulfil the definition of an AE or SAE.
- 8. For non-efficacy studies involving marketed products in established indications, include:
- 9. The signs, symptoms, and/or clinical sequelae resulting from lack of efficacy will be reported as AE or SAE if they fulfil the definition of an AE or SAE. Also, "lack of efficacy" or "failure of expected pharmacological action" also constitutes an AE or SAE.

Page: 68 of 86

Events NOT Meeting the AE Definition

- 1. Any laboratory findings outside of the normal range or other abnormal safety assessments which are associated with the underlying disease, unless judged by the investigator to be more severe than expected for the participant's condition.
- 2. The disease/disorder being studied or expected progression, signs, or symptoms of the disease/disorder being studied, unless more severe than expected for the participant's condition.
- 3. Medical or surgical procedure (e.g., endoscopy, appendectomy): the condition that leads to the procedure is the AE.
- 4. Situations in which an untoward medical occurrence did not occur (social and/or convenience admission to a hospital).
- 5. Anticipated day-to-day fluctuations of pre-existing disease(s) or condition(s) present or detected at the start of the study that do not worsen.

10.3.2 Definition of SAE

If an event is not an AE per definition above, then it cannot be an SAE even if serious conditions are met (e.g., hospitalization for signs/symptoms of the disease under study, death due to progression of disease).

An SAE is defined as any untoward medical occurrence that, at any dose:

Results in death

Is life-threatening

The term 'life-threatening' in the definition of 'serious' refers to an event in which the participant was at risk of death at the time of the event. It does not refer to an event, which hypothetically might have caused death, if it were more severe.

Requires inpatient hospitalization or prolongation of existing hospitalization

In general, hospitalization signifies that the participant has been detained (usually involving at least an overnight stay) at the hospital or emergency ward for observation and/or treatment that would not have been appropriate in the physician's office or outpatient setting. Complications that occur during hospitalization are AEs. If a complication prolongs hospitalization or fulfills any other serious criteria, the event is serious. When in doubt as to whether "hospitalization" occurred or was necessary, the AE should be considered serious.

Hospitalization for elective treatment of a pre-existing condition that did not worsen from baseline is not considered an AE.

Results in persistent disability/incapacity

- 1. The term disability means a substantial disruption of a person's ability to conduct normal life functions.
- 2. This definition is not intended to include experiences of relatively minor medical significance such as uncomplicated headache, nausea, vomiting, diarrhea, influenza, and accidental trauma (e.g., sprained ankle) which may interfere with or prevent everyday life functions but do not constitute a substantial disruption.

Page: 69 of 86

Is a congenital anomaly/birth defect

Other situations:

- 1. Medical or scientific judgment should be exercised in deciding whether SAE reporting is appropriate in other situations such as important medical events that may not be immediately life-threatening or result in death or hospitalization but may jeopardize the participant or may require medical or surgical intervention to prevent one of the other outcomes listed in the above definition. These events should usually be considered serious.
- 2. Examples of such events include invasive or malignant cancers, intensive treatment in an emergency room or at home for allergic bronchospasm, blood dyscrasias or convulsions that do not result in hospitalization, or development of drug dependency or drug abuse.

10.3.3 Recording and Follow-up of AE and/or SAE

AE and SAE Recording

- 1. When an AE/SAE occurs, it is the responsibility of the investigator to review all documentation (e.g., hospital progress notes, laboratory reports, and diagnostics reports) related to the event.
- 2. The investigator will then record all relevant AE/SAE information in the CRF.
- 3. It is **not** acceptable for the investigator to send photocopies of the participant's medical records to the Sponsor in lieu of completion of the AE/SAE CRF page.
- 4. There may be instances when copies of medical records for certain cases are requested by the Sponsor. In this case, all participant identifiers, with the exception of the participant number, will be redacted on the copies of the medical records before submission to the CRO/Sponsor.
- 5. The investigator will attempt to establish a diagnosis of the event based on signs, symptoms, and/or other clinical information. Whenever possible, the diagnosis (not the individual signs/symptoms) will be documented as the AE/SAE.

Assessment of Intensity

- 1. The intensity of AEs should be documented using the National Cancer Institute's Common Terminology Criteria for Adverse Events (NCI-CTCAE, v.5.0).
- 2. The intensity of AEs is classified according to the following categories for events not listed in the CTCAE v.5.0:
- 3. Grade 1: Mild; asymptomatic or mild symptoms; clinical or diagnostic observations only; intervention not indicated.
- 4. Grade 2: Moderate; minimal, local or noninvasive intervention indicated; limiting age-appropriate instrumental ADL (ADL: Activities of Daily Living; instrumental ADL refer to preparing meals, shopping for groceries or clothes, using the telephone, managing money, etc.).
- 5. Grade 3: Severe or medically significant but not immediately life-threatening; hospitalization or prolongation of hospitalization indicated; disabling; limiting self-care ADL (Self-care ADL refer to bathing, dressing and undressing, feeding self, using the toilet, taking medications, and not bedridden).
- 6. Grade 4: Life-threatening consequences; urgent intervention indicated.

Page: 70 of 86

Assessment of Causality

- 1. The investigator is obligated to assess the relationship between study treatment and each occurrence of each AE/SAE.
- 2. A "reasonable possibility" of a relationship conveys that there are facts, evidence, and/or arguments to suggest a causal relationship, rather than a relationship cannot be ruled out.
- 3. The investigator will use clinical judgment to determine the relationship.
- 4. Alternative causes, such as underlying disease(s), concomitant therapy, and other risk factors, as well as the temporal relationship of the event to study treatment administration will be considered and investigated.
- 5. The investigator will also consult the Investigator's Brochure (IB) and/or Product Information, for marketed products, in his assessment.
- 6. For each AE/SAE, the investigator **must** document in the medical notes that he has reviewed the AE/SAE and has provided an assessment of causality.
- 7. There may be situations in which an SAE has occurred, and the investigator has minimal information to include in the initial report to the Sponsor. However, it is especially important that the investigator always assesses causality for every event before the initial transmission of the SAE data to the Sponsor.
- 8. The investigator may change his opinion of causality in light of follow-up information and send a SAE follow-up report with the updated causality assessment.
- 9. The causality assessment is one of the criteria used when determining regulatory reporting requirements.

Follow-up of AEs and SAEs

- 1. The investigator is obligated to perform or arrange for the conduct of supplemental measurements and/or evaluations as medically indicated or as requested by the Sponsor to elucidate the nature and/or causality of the AE or SAE as fully as possible. This may include additional laboratory tests or investigations, histopathological examinations, or consultation with other health care professionals.
- 2. If a participant dies during participation in the study or during a recognized follow-up period, the investigator will provide the Sponsor with a copy of any post-mortem findings including histopathology.
- 3. New or updated information will be recorded in the originally completed CRF.
- 4. The investigator will submit any updated SAE data to the Sponsor within 24 hours of receipt of the information.

Page: 71 of 86

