The effect of monotherapy with enzalutamide and apalutamide in patients with hormone-naïve prostate cancer has been explored and reported. A single arm phase 2 study by Tombal et al evaluating enzalutamide monotherapy in men with biochemically recurrent and hormonesensitive metastatic prostate cancer showed similar PSA level reduction by enzalutamide monotherapy compared to testosterone suppression treatment with luteinizing hormonereleasing hormone (LHRH) analogues. Enzalutamide alone, however, resulted in a mean increase of testosterone levels of 114% at week 25 with frequent side effects of grades 1-2 such as gynecomastia (36%), fatigue (33%), nipple pain (20%), and hot flush (18%) (Tombal et al. 2014). In this enzalutamide study, peak serum testosterone rise plateaued at around 10 to 13 weeks of treatment. At ASCO 2020, (Maluf et al. 2018) presented data of LACOG 0415, a three-arm phase 2 study exploring efficacy of the ADT-free alternatives in a patient population with advanced hormone-sensitive prostate cancer and biochemical recurrence. The apalutamide monotherapy arm demonstrated similar PSA decline level to the other two arms, however, it too resulted in a high mean increase in levels of serum testosterone of 134.3% at week 25 with high incidences of any grade side effects such as gynecomastia (55%), rash (26%), fatigue (21%), pruritus (17%) and breast pain (14%). In this apalutamide study, peak serum testosterone rise plateaued at around 10 to 13 weeks of treatment.

The increased serum testosterone levels are peripherally converted to estrogens (Fagerlund et al. 2015, Scher et al. 1997) and are suspected to be the cause for the specific feminization side effects like gynecomastia and breast tenderness observed in the above mentioned two trials.

The increase in serum testosterone level observed with enzalutamide and apalutamide is thought to result from the ability of these compounds to penetrate the blood-brain-barrier (BBB), resulting in upregulation of luteinizing hormone signaling due to blockage of the androgen receptor in hypothalamus and pituitary gland which increases testosterone production. Unfortunately, it is not fully established whether this negative feedback loop occurs entirely within the central nervous system (CNS) or whether parts of it may be situated outside of the BBB.

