The conduct of the randomized phase is binding to a condition of obtaining an estimated mean percent increase from baseline in serum testosterone level at 12 weeks of less than 45%, and non-binding to a condition that the incidence of feminizing side effects observed is below that previously reported (CC)

The Sponsor reserves the right to conduct or stop the lead-in phase in case data on testosterone levels from patients treated with darolutamide alone would become available from other ongoing studies.

Page: 20 of 86

1.4.1.2 Randomized phase:

A maximum of 40 participants (20 per arm) will be randomly assigned to study treatment (darolutamide or enzalutamide) such that approximately 34 evaluable participants complete the study. The randomized stage will require a sample size of 20 per group to provide 85% power to test the null hypothesis of no-difference between groups on mean percent change at two-sided 0.05 level. This assessment is based on a mean percent change in serum testosterone from baseline and Standard Deviation for the darolutamide arm of 45% and 65% versus 110% and 75% respectively for enzalutamide. The final sample size and time of testosterone assessments may be modified according to the results of the lead-in phase.

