9.4.2.1 Lead-in Phase

For testosterone at the visits at week 24 and 52, the differences between the log transformed data at the visit and that at baseline will be estimated with 95% confidence intervals using SAS PROC MIXED with the ESTIMATE statement and a Toeplitz covariance structure.

These are to be transformed to mean percent change and 95% confidence intervals using the same steps as for the primary analysis in the lead-in phase. Results will be summarized in a similar manner to the primary endpoint for testosterone at week 24 and 52. PSA response rates will be summarized at week 4, 12, 24, 36 and 52 using frequencies and percentages. Response levels to be summarized will be 30%, 50% and 90% decreases.

Feminizing side effects of gynecomastia, breast tenderness/pain, nipple pain, and hot flush will be summarized using frequencies and percentages.

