9.4.2.2 Randomized Phase

For testosterone at the visits at week 24 and 52, and for each of the sex hormones, and for each of the components of fat and glucose metabolism at weeks 4, 12, 24 and 52, the differences between the log transformed data at the visit and that at baseline will be compared across treatment groups with 95% Confidence Intervals using SAS PROC MIXED with the SLICE option and a Toeplitz covariance structure. These are to be transformed to the ratio of the fold change from baseline for darolutamide to that for enzalutamide and 95% confidence intervals using the same steps as for the primary analysis in the randomized phase. Results will be analyzed in a similar manner to the primary endpoint for testosterone at week 24 and 52 and for the other sex hormones and the metabolic endpoints. These analyses will be summarized graphically using the mean percent change over time with 95% confidence intervals at each visit by treatment group, flagging visits where differences are significant at the nominal 0.05 and 0.01 levels.

Page: 61 of 86

PSA response rates will be compared descriptively across treatments at week 4, 12, 24, 36 and 52 using frequencies and percentages. Response levels to be summarized will be 30%, 50% and 90% decreases.

Differences in the FACT-P prostate cancer subscale will be summarized at each visit using PROC Mixed with the SLICE option and the mean subscale score will be depicted graphically over time with 95% confidence intervals at each visit by treatment group, flagging visits where differences are significant at the nominal 0.05 and 0.01 levels.

Feminizing side effects of gynecomastia, breast tenderness/pain, nipple pain, and hot flush will be summarized using frequencies and percentages by treatment group.

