All grades of the feminizing side effects of gynecomastia (including breast enlargement, breast mass, breast swelling), breast tenderness/pain, nipple pain, and hot flush will be summarized using frequencies and percentages. Incidence of AEs of special topics (Bone fractures excluding pathological fractures, Cerebral ischemia, Diabetes mellitus and Hyperglycaemia, Fall, Fatigue/ asthenic conditions, Weight decreased, Rash, Seizure, Hypertension, Vasodilatation and flushing, Mental impairment disorders, Depressed mood disorders, Breast disorders/gynecomastia, Cardiac disorders, Cerebral and intracranial hemorrhage) associated with ARI treatment will also be presented.

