4.3.1.2 Randomized Phase

• Testosterone at weeks 24 and 52:

The differences between the log transformed data at the visit and baseline will be compared across treatment groups with 95% Confidence Intervals using SAS PROC MIXED with the SLICE option and a Toeplitz covariance structure. These will be

ARAMON V3.0 Page: 16 of 31

transformed to the ratio of the fold change from baseline for darolutamide to that for enzalutamide and 95% confidence intervals using the same steps as for the primary analysis in the randomized phase. SAS code will be similar to code shown in Appendix 6: Randomized phase analysis for natural logarithm transformed Testosterone and other endpoints using the log transformation. Results will be summarized in a similar manner to the primary endpoint and will be summarized graphically using the mean percent change over time with 95% confidence intervals at each visit by treatment group, flagging visits where differences are significant at the nominal 0.05 and 0.01 levels.

• Sex hormones:

Will be analyzed at week 4, 12, 24 and 52 similar to testosterone.

• Components of fat and glucose metabolism:

Will be analyzed at week 4, 12, 24 and 52 similar to testosterone.

PSA responses

Will be compared descriptively across treatments at weeks 4, 12, 24, 36 and 52 using frequencies and percentages.

• FACT-P

Differences in the FACT-P prostate cancer subscale and total will be summarized at each visit using PROC Mixed with the SLICE option, and the mean subscale and total scores will be depicted graphically over time with 95% confidence intervals at each visit by treatment group, flagging visits where differences are significant at the nominal 0.05 and 0.01 levels. The scoring procedure for FACT-P is elaborated in Appendix 2: Scoring procedures for FACT-P.

• Analysis of AEs:

All grades of the feminizing side effects of gynecomastia (including breast enlargement, breast mass, breast swelling), breast tenderness/pain, nipple pain, and hot flush, will be summarized using frequencies and percentages by treatment group.

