4.5.2 Adverse Events

Treatment-emergent AE (TEAE) is defined as any event arising or worsening after the first dose of study drug until 30 days after the last dose of study drug.

An overview of TEAEs will be summarized for the appropriate safety analysis set at the three data cuts. The following summaries will be done.

- Overview of TEAEs
- TEAEs by MedDRA ad worst CTCAE grade
- TEAEs by MedDRA ad worst CTCAE grade 3, 4 or 5
- TEAEs: number of subjects by primary SOC and PT
- TEAEs leading to permanent discontinuation of study drug: number of subjects by primary SOC and PT
- Number of subjects with TEAE by PT in decreasing order
- Drug-related TEAEs: number of subjects by primary SOC and PT

• Drug-related TEAEs leading to permanent discontinuation of study drug: number of subjects by primary SOC and PT

Page: 18 of 31

- Number of subjects with drug-related TEAE by PT in decreasing order
- SAEs: number of subjects by primary SOC and PT
- TESAEs: number of subjects by primary SOC and PT
- Drug-related TESAEs: number of subjects by primary SOC and PT
- TE non-SAEs (excluding TESAEs): number of subjects by primary SOC and PT

Additionally, feminizing side effects as described in Section 4.3, will be summarized by

- Overview of TEAEs of feminizing side effects
- Number of subjects with TEAEs of feminizing side effects by PT in decreasing order
- Treatment-emergent study drug-related adverse events of feminizing side effects by MedDRA SOC and PT and worst CTCAE grade
- Number of subjects with TEAEs of feminizing side effects leading to permanent discontinuation of study drug by PT in decreasing order
- Number of subjects with drug-related TEAEs of feminizing side effects by PT in decreasing order
- Number of subjects with drug-related TEAEs of feminizing side effects leading to permanent discontinuation of study drug by PT in decreasing order
- SAEs of feminizing side effects: number of subjects by primary SOC and PT
- TESAEs of feminizing side effects: number of subjects by primary SOC and PT
- Drug-related TESAEs of feminizing side effects: number of subjects by primary SOC and PT

AEs of special topics will be summarized by

• Number of subjects with special topics for adverse events

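### The diagnosis-over-symptoms AE recording rule may cause breast and nipple pain to be under-recorded in men with gynecomastia, although both are to be reported as separate feminizing events

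*Protocol*

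**What the plan says.** **Recording.** Protocol 10.3.3, AE and SAE Recording, item 5, asks the investigator to establish a diagnosis from signs, symptoms and other clinical information, and continues: "Whenever possible, the diagnosis (not the individual signs/symptoms) will be documented as the AE/SAE".

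**Analysis.** Protocol 9.4.2.1 plans for the lead-in: "Feminizing side effects of gynecomastia, breast tenderness/pain, nipple pain, and hot flush will be summarized using frequencies and percentages". Protocol 9.4.2.2 plans the same by treatment group. SAP 4.3.1.1 and 4.3.1.2 fold some findings into gynecomastia but keep the pain terms apart: "All grades of the feminizing side effects of gynecomastia (including breast enlargement, breast mass, breast swelling), breast tenderness/pain, nipple pain". SAP 4.5.2 adds tables by preferred term, for example: "Number of subjects with TEAEs of feminizing side effects by PT in decreasing order". SAP 4.6.2 repeats a by-term table in the lead-in for two subgroups of testosterone increase.

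**Use.** Protocol 1.4.1.1 makes the start of the randomized phase "non-binding to a condition that the incidence of feminizing side effects observed is below that previously reported"; 4.1 says much the same. The enzalutamide rates cited in Protocol 1.2 give gynecomastia (36%) and nipple pain (20%) as separate items. Protocol 2.2 and 2.2.1.4 give nipple pain as 19%.

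**Other provisions.** Protocol 8.7.2 prefers open-ended questioning, 8.7.7 names no AEs of special interest, and 8.8 schedules full physical examinations only at baseline and EOT. No breast-symptom checklist is described.

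**The concern.** A rate by preferred term is only as complete as the terms that sites enter. The planned tables need breast pain and nipple pain as entries in their own right. The recording rule tells sites, where they can, to enter one diagnosis in place of its symptoms. An investigator who sees breast or nipple pain in a man with gynecomastia can reasonably follow item 5 and enter gynecomastia alone. The pain then cannot be restored at analysis.

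Feminizing effects are the clinical consequence that the trial expects to be less frequent with darolutamide, so these rates will be read closely. In the lead-in, a low pain rate could make the non-binding condition easier to meet for reasons unrelated to the drug, if that condition is judged term by term. In the randomized phase, the loss need not be equal in the two arms.

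**Working it through.** The documents state no target, power or error rate for feminizing events, so there is no plan figure to reproduce. The check asks which rates are exposed, in which direction, and how far they could move.

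**Inputs from the documents.** Gynecomastia g = 36%; nipple pain p = 20% (19% in some sections); 25 men in the lead-in; 20 per arm in the randomized phase.

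**Assumed, because not in the documents.** The overlap o = P(pain and gynecomastia), which can lie anywhere from 0% to 20%; and the absorption share s, meaning the fraction of men with both whose pain is not entered.

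**Direction.** Recorded pain rate = p − s·o. Neither s nor o can be negative, so the recorded rate never exceeds the true one. A man whose pain is absorbed still counts under gynecomastia, so the gynecomastia rate and the any-feminizing-event count do not change. Hot flush is not involved.

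**Size, nipple pain (p = 20%).**

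| Overlap | o | s = 0.5 | s = 1 |
|---|---|---|---|
| None | 0% | 20.0% | 20.0% |
| Independent | 0.36 × 0.20 = 7.2% | 16.4% | 12.8% |
| Half of men with pain have gynecomastia | 10% | 15.0% | 10.0% |
| All men with pain have gynecomastia | 20% | 10.0% | 0% |

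With p = 19% and s = 1, the last column reads 19.0%, 12.2%, 9.5% and 0%.

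**Lead-in condition, read term by term.** Take 25 men whose true rates equal the quoted 36% and 20%. The binomial chance of observing nipple pain below 20% (4 of 25 or fewer) is 42% with full recording. Under independence it is 61% at s = 0.5 and 79% at s = 1. With half overlap it is 68% and 90%. If gynecomastia must also fall below 36% (8 of 25 or fewer), the multinomial chance that both do rises, at s = 1, only from 18% to 30% (independent), 20% to 36% (half overlap) or 29% to 43% (full overlap).

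**Randomized phase.** Let pain occur in a fraction a of men with gynecomastia and b of the others, with a, b and s the same in both arms. Then

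- true pain = a·g + b·(1 − g)
- loss = s·a·g, which is proportional to g
- recorded difference = (g_E − g_D)·[a(1 − s) − b]

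For a > b, the recorded difference therefore changes sign only when s > 1 − b/a. Illustration with assumed a = 40%, b = 8.75%, and gynecomastia 36% (enzalutamide) vs 10% (darolutamide):

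| s | Enzalutamide pain | Darolutamide pain | Difference |
|---|---|---|---|
| 0 | 20.0% | 11.9% | +8.1 points |
| 0.5 | 12.8% | 9.9% | +2.9 points |
| 1 | 5.6% | 7.9% | −2.3 points |

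On these inputs reversal needs s > 1 − 0.0875/0.40 = 0.78. If pain occurs only in men with gynecomastia (b = 0), both arms lose the same proportion and the difference shrinks without reversing. If gynecomastia is equally common in the arms, the loss is equal.

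**Sampling error for scale.** The exact 95% interval for 4 of 20 is 5.7% to 43.7%, wider than most of these shifts.

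**The case against.** The best defence is that item 5 need not bite. It applies only where possible, and no section says that breast or nipple pain is a symptom of gynecomastia. Protocol 1.2 presents them side by side as effects of raised estrogen, and the AE definition in 10.3.1 lets a symptom be an AE. An investigator can enter both without breaching the rule. Pain reported before gynecomastia is diagnosed may already be on file, and nothing tells sites to withdraw it. All of this stands. A reader might infer that pain in every man with gynecomastia goes unrecorded, so that the pain rates count only men without it. The documents support a risk of this, not a certainty.

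Nor does the wording support a claim that the lead-in decision is biased. The condition is non-binding; the binding one concerns testosterone. The comparison is partly blacked out, so term-by-term judgement is an assumption, and SAP 4.5.2 also has an overall overview of feminizing events that is unaffected. The documents do not say how the cited enzalutamide study recorded symptoms; under a similar rule its nipple-pain rate would be low as well. Even on a term-by-term reading, the effect is much smaller once gynecomastia must also pass.

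The comparison between arms is descriptive and small. At full absorption, 5.6% vs 7.9% of 20 men is about 1.1 vs 1.6 men.

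What survives is that sites are given a general rule that conflicts with tables needing the detail, with no exemption in either document. Sampling error will show in the denominators; this loss would not, and it runs in one direction.

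**Conclusion.** The recording rule and the planned tables need to be reconciled. The exposure is limited to breast tenderness/pain and nipple pain. It would be wrong to say that all the separate feminizing-event rates are biased low.

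The size cannot be fixed from the documents. At the quoted 36% and 20% with independence, nipple pain would be recorded at 16.4% (half absorption) or 12.8% (full absorption); across all overlaps and absorption shares the range is 0% to 20%.

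The absolute loss is larger in the arm with more gynecomastia only if absorption and the risk of pain given gynecomastia are similar across arms. That this arm will be enzalutamide is the trial's hypothesis. If it is, the pain difference shrinks, to darolutamide's disadvantage. A reader might infer that the difference will reverse; on the illustrated inputs that needs more than about 78% absorption, and those inputs are assumptions. The matter is inexpensive to correct and best settled before the randomized phase.

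**What to change.** Add an exception to Protocol 10.3.3 item 5 and repeat it in the CRF completion guideline: *gynecomastia (including breast enlargement, mass or swelling), breast tenderness/pain, nipple pain and hot flush are each entered as a separate AE when present, even if one is considered a symptom of another.*

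For lead-in data already collected under the present rule, report the separate breast-pain and nipple-pain rates as possible lower bounds and rely on the gynecomastia rate for comparison with earlier reports. A composite of breast events should not be set against the cited enzalutamide rates: the documents give only separate rates, and the composite of 36% and 20% could lie anywhere from 36% (pain wholly within gynecomastia) to 56% (no overlap).

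The cost is one sentence in each of two documents, a few more AE lines for affected men, and slightly higher reported pain rates.
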